IND	Investigational New Drug
IRB	institutional review board
IULN	institutional upper limit of normal
CCI	
mAb	monoclonal antibody
MTD	maximum tolerated dose
NSAE	non-serious adverse event
NCI	National Cancer Institute
NSAID	non-steroidal anti-inflammatory drug
OR	Objective Response, OR = CR + PR
PBS	phosphate-buffered saline
PK	pharmacokinetics
PR	partial response
RBC	red blood cell
SAE	serious adverse event
Trop-2	Trophoblastic cell-surface antigen
TPP	time to progression
WBC	white blood cell

1. INTRODUCTION

Over the past 60 years, antibodies have been investigated for their ability to shepherd toxic compounds, such as radioactivity, drugs, or toxins to tumors in an attempt to deliver these agents in a more selective manner for improved anti-tumor effects. While initially finding unconjugated antibodies to be largely ineffective, today there are several antibodies approved for clinical use in a variety of cancers, and there are many more under clinical evaluation.⁽¹⁻⁶⁾ Even though relatively few antibody conjugates have been approved for treating cancer, most antibodies are themselves incapable of eliciting sufficient responses to warrant their use as standalone agents. Instead, most unconjugated antibodies are combined with chemotherapeutic regimens in some way. Thus, it is not surprising that there has been a renewed interest in antibody-drug conjugates, particularly with the recent success of the trastuzumab emtansine, an anti-HER2- maytansine conjugate, in HER2-positive breast cancer patients, even those who were refractory to unconjugated trastuzumab.⁽⁷⁻⁹⁾

[figure not shown]
Most of the antibody-drug conjugates (ADC) being explored clinically today use drugs that cannot be given alone because they are too toxic (i.e., ultra-toxic). Conjugating these drugs, such as maytansine, calicheamicin, and auristatin to antibodies detoxifies them, usually by altering their natural pharmacokinetic and biodistribution properties. However, as the decision to remove Mylotarg (gemtuzumab ozogamicin; anti-CD33-calicheamicin conjugate) from marketing suggests, the therapeutic window of these agents can be limited.^(10, 11) For this reason, we have taken a closer look at the various chemotherapeutic agents that already have been tested clinically to determine if any might be suitable for conjugation to antibodies. Since most chemotherapeutics require micromolar concentrations for therapy, they are not suitable for use as antibody conjugates. However, SN-38 is promising because it has activity in the low nanomolar range, which is between the extreme of the ultratoxics that are active in subnanomolar concentrations and most of the other commonly used chemotherapeutics.

SN-38, a topoisomerase I inhibitor, is the active metabolite of the camptothecin CPT-11 (irinotecan), which is approved as a single agent for colorectal cancer and included in treatment regimens such as FOLFIRI.⁽¹²⁻²⁰⁾ SN-38 is not water soluble, and therefore it was derivatized to a water-soluble form, irinotecan, but it must be enzymatically cleaved to the SN-38 form for it to have maximum potency. Unfortunately, at best, only 5% of irinotecan will be converted to the active SN-38 form by esterase activity residing primarily in the liver, albeit there are esterases in the tumor that can cleave irinotecan to SN-38.⁽²¹⁻²⁴⁾ Its catabolism in the liver results in its transport through the bile duct into the intestines, resulting in GI toxicity.

[figure not shown]
CCI

A large block of text has been redacted with black bars. The word 'CCI' is printed in red at the top of this redacted area.

CCI

Immunomedics is currently pursuing several ADCs based on the SN-38 conjugation technology it developed. In this protocol, a humanized anti-Trop-2 antibody (hRS7) is examined. Trop-2 (trophoblastic cell-surface antigen; also known as EGP-1, epithelial glycoprotein-1), is a cell surface, transmembrane calcium signal transducer glycoprotein belonging to the TACSTD gene family that is highly expressed in many epithelial cancers, particularly metastatic sites⁽²⁷⁾, with much lower expression in normal tissues.⁽²⁸⁾ Trop-2 has been implicated as an important antigen in oncogenesis, often being found in more aggressive tumors⁽²⁹⁻³⁹⁾. The murine RS7 antibody was initially identified as being specific for epithelial glycoprotein-1 (aka, Trop-2)^(40, 41), being found in a number of different epithelial cancers and it was internalized⁽⁴²⁻⁴⁵⁾, a highly desirable property for an antibody-drug conjugate. Indeed, as mentioned above, the initial studies with the SN-38 conjugates used an anti-CEACAM5 antibody that is not readily internalized, yet it was potent *in vivo*, leaving us to hypothesize that local release of the SN-38 from the antibody bound to the tumor provides an important mechanism for that conjugate's activity. However, the hRS7-SN-38 conjugate further benefits from the antibody's ability to internalize.⁽⁴⁶⁾

Horizontal bar chart showing CCI values for 15 countries. The y-axis lists countries: CCI, Argentina, Brazil, Chile, Colombia, Costa Rica, Ecuador, El Salvador, Guatemala, Honduras, Mexico, Nicaragua, Panama, Paraguay, Uruguay, and Venezuela. The x-axis represents the CCI value, with a scale from 0 to 100. Most countries have high CCI values (above 80), while Argentina and Venezuela have lower values (around 60).

Country	CCI
CCI	85
Argentina	60
Brazil	95
Chile	98
Colombia	92
Costa Rica	95
Ecuador	95
El Salvador	95
Guatemala	95
Honduras	95
Mexico	95
Nicaragua	95
Panama	95
Paraguay	95
Uruguay	95
Venezuela	60

Since 8 of the 9 patients treated at 12 mg/kg required dose delays and reductions during the first cycle, that starting dose was considered to have exceeded the maximum acceptable dose for further consideration. In contrast, the initial dose level of 8 mg/kg appears acceptable with 3 additional patients (2 pancreatic, 1 gastric cancer). To establish a maximum acceptable dose level, a final intermediate dose level of 10 mg/kg was evaluated.

Based upon these data from the Phase I portion of this study, starting doses of 8 or 10 mg/kg, administered on days 1 and 8 of a 21-day cycle were considered acceptable for further evaluation, and subsequently 10 mg/kg was selected for the ongoing Phase II portion of this study. Severe (Grade 3 or higher) toxicities have primarily included neutropenia, diarrhea and febrile neutropenia. Adverse events of all causalities (all grades and grade 3/4) are shown below.

Adverse events all grades and all causalities with incidence ≥ 5%.					
Adverse Event Preferred Term	All Doses (N=203)	8 mg/kg (N=82)	10 mg/kg (N=109)	12 mg/kg (N=9)	18 mg/kg (N=3)
Nausea	36%	52%	22%	56%	100%
Diarrhea	35%	48%	19%	67%	67%
Fatigue	35%	54%	17%	89%	67%
Neutropenia	30%	38%	17%	89%	100%
Alopecia	29%	41%	18%	44%	33%
Vomiting	23%	28%	17%	44%	67%
Anemia	20%	34%	7%	33%	33%
Abdominal pain	17%	18%	13%	33%	67%
Constipation	16%	27%	9%	22%	0%
Anorexia	12%	17%	8%	0%	33%
Hypokalemia	10%	13%	6%	33%	33%
Hypomagnesemia	10%	12%	6%	22%	67%
Edema peripheral	10%	16%	4%	22%	33%
Pyrexia	9%	15%	4%	22%	0%
Dizziness	8%	12%	5%	22%	0%
Dyspnea	8%	15%	4%	11%	0%
Headache	7%	13%	4%	0%	0%
Leukopenia	7%	11%	4%	22%	0%

Grade 3 and 4 adverse events all causalities ≥ 1%.					
Adverse Event Preferred Term	All Doses (N=203)	8 mg/kg (N=82)	10 mg/kg (N=109)	12 mg/kg (N=9)	18 mg/kg (N=3)
Neutropenia	22%	29%	13%	56%	67%
Febrile neutropenia	4%	2%	5%	11%	0%
Diarrhea	3%	4%	4%	22%	0%
Anemia	2%	10%	2%	22%	0%
Fatigue	2%	7%	2%	22%	0%
Abdominal pain	2%	2%	1%	0%	67%
Leukopenia	2%	5%	3%	0%	0%
Hypokalemia	1%	2%	1%	11%	0%
Hyponatremia	1%	4%	1%	0%	0%
Lymphopenia	1%	2%	1%	0%	0%
Nausea	1%	1%	1%	0%	0%
Urinary tract infection	1%	1%	1%	0%	0%
Vomiting	1%	1%	1%	0%	0%

In Phase I & Phase II, there was evidence of efficacy. Partial responses have been observed currently in patients with triple-negative breast cancer, small-cell lung cancer, non-small-cell lung cancer, esophageal cancer, urinary bladder, and colorectal cancer. Disease stabilization has been observed in many patients.

2. STUDY OBJECTIVES

This is a first-in-man clinical study with the antibody-drug conjugate, IMMU-132, which uses the humanized antibody hRS7 to deliver the topoisomerase I inhibitor, SN-38, directly to Trop-2-expressing epithelial tumors.

2.1. Primary Objective

The primary objective in Phase I is to evaluate the safety and tolerability of IMMU-132 as a single agent administered in 3-week treatment cycles, in previously treated patients with advanced epithelial cancer. Dose escalation in Phase I (completed) was intended to determine a maximum acceptable dose and select cancer types for continued expanded study in Phase II. Phase II continues enrollment with dose levels and cancers selected based upon Phase I results and preliminary efficacy results. The primary objective in Phase II is the evaluation of the safety and efficacy of IMMU-132 administered in 3-week treatment cycles, at a dose selected in Phase I.

2.2. Secondary Objectives

In Phase I, the secondary objectives are to obtain initial data concerning pharmacokinetics, immunogenicity, and efficacy with this dosing regimen. In Phase II, secondary objectives also include pharmacokinetics and immunogenicity.

3. STUDY DESIGN

This is a Phase I/II, open-label study of IMMU-132 in previously treated patients with the following metastatic epithelial cancers:

- Gastric adenocarcinoma (GC)
- Esophageal cancer (EC)
- Hepatocellular carcinoma (HCC)
- Non-small cell lung cancer (NSCLC)
- Small-cell lung cancer (SCLC)
- Epithelial ovarian cancer (EOC)
- Cervical Cancer
- Papillary thyroid cancer
- Glioblastoma multiforme (GBM)
- Endometrial Cancer
- Triple-negative breast cancer (TNBC)
- Non-triple-negative breast cancer (mBC)
- Hormone-refractory prostate cancer (HRPC)
- Head and neck cancers- squamous cell (SCCHN)
- Renal cell carcinoma (clear cell) (RCC)
- Urothelial cancers, including urinary bladder cancer.

A table of approved or standard therapeutic regimens or regimens in documented clinical trials for each of these cancer types is included in **Appendix 1**. *Patients who have not received all approved or standard treatments for their cancer must be informed that these alternatives to receiving IMMU-132 are available prior to consenting to participate in this trial.*

In Phase II, up to 150 patients (assessable) in each of 5 cancer subtypes (TNBC, non-TNBC, NSCLC, SCLC, UC) and up to 56 patients (assessable) per other cancer types will be studied at the 10 mg/kg dose.

Based upon the Phase I results, the 8 mg/kg and 10 mg/kg dose levels were selected for further evaluation in Phase II, and subsequently the 10 mg/kg dose was selected for the ongoing Phase II study.

Baseline evaluations within 4 weeks of the scheduled start of treatment include patient history, physical examination with vital signs and performance evaluation, local histology review to confirm one of the epithelial cancers listed above, contrast-enhanced CT or MRI scans (chest, abdomen, pelvis with additional imaging of other involved areas), CBC (with differential and platelet count), routine serum chemistries, urinalysis, PT/PTT, EKG, and serum samples for human anti-human antibody (HAHA). **CCI**

CCI

CCI

CCI

A single whole-blood sample (purple or pink-topped tube, 2 mL) will be collected from each registered patient prior to receiving IMMU-132 for determination of *UGT1A1* or other *UGT1* genotype. This sample will be shipped to Sponsor who will perform this assay. The results are not used to establish eligibility but will be used for retrospective assessment of toxicity.

All patients receive two doses of IMMU-132 administered in 3-week treatment cycles with weekly dosing in the first two weeks (days 1 and 8 of 21-day cycles) and no dosing the third week. In the ongoing Phase II portion of the study, all patients receive 10 mg/kg starting doses and the treatment cycles are to be continued in the absence of unacceptable toxicity or progression of disease requiring termination of further treatment. The first determination of disease progression per RECIST1.1 does not require discontinuation of study treatment if there is still the potential for patient benefit in the opinion of the investigator, but treatment must be discontinued if subsequent imaging documents disease progression from that assessment. All patients are closely monitored over the course of their treatment, and NCI CTCAE v4.0 is used to grade all adverse events and to provide dose reduction, delay or cessation guidelines in the event of treatment-related toxicity. Based on irinotecan and animal testing, the major toxicity of IMMU-132 is expected to be gastrointestinal symptoms and hematologic suppression. Growth factors and other supportive care are allowed when medically necessary any time during treatment with IMMU-132, but not prophylactically before start of treatment with the first IMMU-132 dose in cycle 1.

[figure not shown]
CCI

Patients who exhibit an excessive cholinergic response to IMMU-132 treatment (e.g., abdominal cramping, diarrhea, salivation, etc.) can receive appropriate premedication (e.g., Atropine) for subsequent treatments.

In Phase I, dose guidelines will be followed with a goal of being able to give the first cycle without requiring dose reduction, delay, or discontinuation or cytokine support at the time the second cycle is given.

Study procedures during treatment include physical examination and vital signs, CBC (with differential and platelet count), routine serum chemistries, PT/PTT, serum samples for PK (*to be collected in all patients in the ongoing Phase II study unless an exemption is approved by the Sponsor*) and HAHA, concomitant medications and adverse events, and EKG.

Starting with the initial dose of IMMU-132, CT (or MRI if needed) examinations are to be obtained at 8-week intervals until the occurrence of progression of disease requiring discontinuation of further treatment. For scans showing stable disease, but with substantial or rapid tumor shrinkage near threshold for a partial response, the 8-week interval for the next scan may be shortened at investigator discretion and if discussed with the medical monitor. Confirmatory CT/MRI scans are to be obtained 4 to 6 weeks after an initial partial response and/or 4 to 6 weeks after an initial complete response. If a confirmatory scan is performed the subsequent scans will be scheduled every 8 weeks from the confirmatory scan. Tumor biomarkers are to be obtained at the time of radiologic evaluations. **CCI**

After discontinuing treatment, the patient will undergo an end-of-study evaluation, with additional follow-up only required until resolution or stabilization of any treatment-related toxicity. Additional CT or MRI may be performed at the discretion of the physician to assess disease status as medically indicated.

Long-term follow-up will continue in patients with stable disease or an objective response with evaluations performed every 3 months for up to 2 years or until progression of disease or initiation of other treatment. All patients will be followed every month for survival, which may be by telephone, for no longer than 2 years from final study evaluation.

Patients continuing to benefit from treatment at time of study closure may be eligible to enroll in a rollover study, so they may continue to receive treatment.

(See study calendar for detailed schedule of study procedures)

4. PATIENT POPULATION

The study population comprises previously treated adults with Stage IV (metastatic) epithelial cancers. Eligible patients must satisfy the following entry criteria at time of study entry:

4.1. Inclusion Criteria

- Male or female patients, ≥ 18 years of age, able to understand and give written informed consent.
- Histologically or cytologically confirmed epithelial cancer of one of the following types:
 - Gastric adenocarcinoma (GC)
 - Esophageal cancer (EC)
 - Hepatocellular carcinoma (HCC)
 - Non-small-cell lung cancer (NSCLC) CCI [REDACTED]
[REDACTED]
[REDACTED]
[REDACTED]
 - Small-cell lung cancer (SCLC)
 - Epithelial ovarian cancer (EOC)
 - Cervical Cancer
 - Endometrial Cancer
 - Triple-negative breast cancer CCI [REDACTED]
[REDACTED]
[REDACTED]
[REDACTED]
[REDACTED]
[REDACTED]
 - Non-triple-negative breast cancer
 - Papillary thyroid cancer (*excludes follicular, medullary, Hurthle cell, and anaplastic thyroid cancer*)
 - Glioblastoma multiforme (GBM)
 - Hormone-refractory prostate cancer (HRPC)
 - Head and neck cancers- squamous cell (SCCHN)
 - Renal cell cancer (clear cell) (RCC)
 - Urothelial cancer CCI [REDACTED]
[REDACTED]
[REDACTED]

CCI

- Stage IV (metastatic) disease (except for patients with GBM).
- Refractory to or relapsed after at least one prior standard therapeutic regimen.

(Appendix 1 lists approved or standard chemotherapeutic agents for each cancer type. Patients who have not received all approved or standard treatments for their cancer must be informed that these alternatives to receiving IMMU-132 are available prior to consenting to participate in this trial.)

- Adequate performance status (ECOG 0 or 1) ([Appendix 2](#)).
- Expected survival \geq 6 months.
- Measurable disease by CT or MRI.
- At least 2 weeks beyond treatment (chemotherapy, investigational drugs including small molecular inhibitors, endocrine therapy, immunotherapy and/or radiation therapy) or major surgery and recovered from all acute toxicities to Grade 1 or less (except alopecia).
- At least 2 weeks beyond high dose systemic corticosteroids (however, low dose corticosteroids < 20 mg prednisone or equivalent daily are permitted).
- Adequate hematology without ongoing transfusional support (hemoglobin > 9 g/dL, ANC $> 1,500$ per mm 3 , platelets $> 100,000$ per mm 3).
- Adequate renal and hepatic function (creatinine $\leq 2.0 \times$ IULN, bilirubin ≤ 1.5 IULN, AST and ALT $\leq 3.0 \times$ IULN or 5 x IULN if know liver metastases).
- Otherwise, all toxicity at study entry \leq Grade 1 by NCI CTCAE v4.0.

4.2. Exclusion Criteria

- Women who are pregnant or lactating.
- Women of childbearing potential and fertile men unwilling to use effective contraception during study until conclusion of 12-week post-treatment evaluation period.
- Patients with Gilbert's disease.
- Patients with brain metastases can be enrolled only if treated, non-progressive brain metastases and off high-dose steroids (> 20 mg prednisone or equivalent) for at least 4 weeks.
- Presence of bulky disease (defined as any single mass > 7 cm in its greatest dimension). Patients with a mass over 7 cm, but otherwise eligible, may be considered for enrollment after discussion and approval with the medical monitor.
- Patients with active \geq grade 2 anorexia, nausea or vomiting, and/or signs of intestinal obstruction.
- Patients with non-melanoma skin cancer or carcinoma *in situ* of the cervix are eligible, while patients with other prior malignancies must have had at least a 3-year disease-free interval.

- Patients known to be HIV positive, hepatitis B positive, or hepatitis C positive.
- Known history of unstable angina, MI, or CHF present within 6 months or clinically significant cardiac arrhythmia (other than stable atrial fibrillation) requiring anti-arrhythmia therapy.
- Known history of clinically significant active COPD, or other moderate-to-severe chronic respiratory illness present within 6 months.
- Prior history of clinically significant bleeding, intestinal obstruction, or GI perforation within 6 months of initiation of study treatment.
- Infection requiring intravenous antibiotic use within 1 week.
- Patients with a history of an anaphylactic reaction to irinotecan or \geq Grade 3 GI toxicity to prior irinotecan.
- Other concurrent medical or psychiatric conditions that, in the Investigator's opinion, may be likely to confound study interpretation or prevent completion of study procedures and follow-up examinations.

4.3. Concomitant Medications and Procedures

- Patients enrolled in this trial will be refractory or relapsed after one or more chemotherapy regimens that may have included irinotecan. All of these treatments must be discontinued for a minimum of 2 weeks prior to starting IMMU-132, and these or other anti-cancer therapies (i.e., drugs, biologics, procedures) are not permitted during this study. However, palliative and/or supportive medications and procedures will be allowed at the investigator's discretion. Patients who receive palliative and/or supportive medications and procedures should have a washout period of 1 week after the last IMMU-132 dose and 2 weeks prior to resuming the treatment with nextIMMU-132 dose, unless otherwise a different washout period is arranged by discussion with medical monitor.
- Premedication with acetaminophen, steroids, and diphenhydramine or equivalents is not anticipated; however, it will be employed as clinically indicated to decrease infusion reactions. Patients with a history of infusional reactions to other antibody therapies may be pre-medicated at the discretion of the treating physician.
- Patients who exhibit an excessive cholinergic response to IMMU-132 treatment (e.g., abdominal cramping, diarrhea, salivation, etc.) can receive appropriate premedication (e.g. Atropine) for subsequent treatments.
- Hematopoietic growth factors or blood transfusions are allowed at physician's discretion, but not prophylactically before the first IMMU-132 dose in Cycle 1.
- High dose systemic corticosteroids are not allowed within 2 weeks of study entry.
- Low dose corticosteroids <20 mg prednisone or equivalent daily are permitted (topical steroids and corticosteroid inhalers are allowed).
- Antiemetics, anti-diarrheal medications, cytokines or blood transfusions may be administered as clinically necessary.
- Other supportive and palliative care is allowed as medically warranted.

CYP3A4 inducers and inhibitors. There is a potential for altered toxicity profile from common medications and foods with possible potent effects on liver metabolism of drugs such as irinotecan and SN38. As such, all patients should be recommended to avoid the following while on study therapy:

CYP 3A4 Inhibitors:

Amiodarone	Indinavir
Amprenavir	Isoniazid
Aprepitant	Itraconazole
Atazanavir	Ketoconazole
Chloramphenicol	Lapatinib
Clarithromycin	Miconazole
Conivaptan	Nefazodone
Cyclosporine	Nelfinavir
Darunavir	Posaconazole
Dasatinib	Ritonavir
Delavirdine	Quinupristin
Diltiazem	Saquinavir
Erythromycin	Tamoxifen
Fluconazole	Telithromycin
Fluoxetine	Troleandomycin
Fluvoxamine	Verapamil
Fosamprenavir	Voriconazole
Grapefruit juice	
Imatinib	

CYP 3A4 Inducers:

Aminoglutethimide	Oxcarbazepine
Bexarotene	Phenobarbital
Bosentan	Phenytoin
Carbamazepine	Primidone
Efavirenz	Rifabutin
Fosphenytoin	Rifampin
Griseofulvin	Rifapentine
Modafinil	St. John's wort
Nafcillin	
Nevirapine	

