7	VS's obtained prior to 1st infusion, every 15 min for the first hour, then every 30 min until completed, at completion, and then 30 min post-infusion In absence of significant changes, may be reduced with subsequent doses to prior to infusion, at 30 min, and then at completion								
8	Ongoing AEs until resolved, new events attributed to test article; otherwise, deaths, hospitalizations, or events requiring IV or prescription anti-infectives or medications related to GI toxicity								
10	CCI								
10	EKG required after completion of day 1 infusion of every even numbered treatment cycle (2, 4, 6, 8, etc) and at the end of the study								
11	PE, Urinalysis, CCI & PT/PTT at baseline, at day 1 of every even numbered treatment cycle (2, 4, 6, 8, etc) and at the end of the study CCI								
12	CCI								
12	Patients who have biopsiable lesion and consented to biopsy will provide as many tumor metastasis biopsy samples as possible								
13	CCI								
NOTE: Unless otherwise specified, collection windows for study time points are nominally within \pm 10% or according to institutional standard procedures. Planned deviations in treatment schedule are allowable up to 7 days due to holidays, vacation or personal reasons.									

TABLE OF CONTENTS

SYNOPSIS.....	2
LIST OF ABBREVIATIONS	15
1. INTRODUCTION	16
2. STUDY OBJECTIVES.....	20
2.1. Primary Objective	20
2.2. Secondary Objectives.....	20
3. STUDY DESIGN.....	21
4. PATIENT POPULATION.....	24
4.1. Inclusion Criteria.....	24
4.2. Exclusion Criteria	25
4.3. Concomitant Medications and Procedures.....	26
5. DOSE ESCALATION	28
6. STUDY PROCEDURES	28
6.1. Informed Consent.....	28
6.2. Patient Registration.....	28
6.3. Pre-Study/Baseline Evaluations	28
6.4. 3-Week Treatment Cycle Procedures.....	30
6.5. Pharmacokinetic Evaluations	31
6.6. Final Study Evaluation or Unscheduled/Early Termination Visit	32
6.7. Long-Term Follow-Up.....	32
6.8. Criteria for Removal from Protocol Treatment.....	33
7. STUDY DRUG INFORMATION	34
7.1. Description of Study Drug	34
7.2. Drug Accountability.....	34
CCI [REDACTED]	
7.4. Study Drug Treatment.....	35
7.4.1. Preventative Medications.....	35
7.4.2. Vital Signs.....	36
7.4.3. Intravenous Administration.....	36
7.4.4. Managing Infusional Toxicity.....	36
7.4.5. Dosing Schedule	39
7.4.6. Dose Reduction and Termination Guidelines	39
7.4.7. Biopsy specimens.....	40

8.	STUDY EVALUATIONS	42
9.	ADVERSE EVENTS	43
9.1.	Serious Adverse Events	43
9.2.	Reporting AEs/SAEs.....	44

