7.4.4. Managing Infusional Toxicity

Immunomedics, Inc., should be notified within 24 hours in the event of any serious infusion reaction.

NCI CTCAE version 4.0 is used to grade all adverse events and to provide management guidelines for infusional toxicity.

For a serious infusion reaction considered severe or life threatening (NCI toxicity Grade 3 or higher) an infusion must be permanently terminated.

- Examples of such events include: serious or clinically significant cardiopulmonary events, severe allergic (symptomatic bronchospasm) or anaphylactic reactions, or other severe reactions.
- The occurrence of Grade 3 infusion-related reactions (e.g., Prolonged infusion related reactions-not rapidly responsive to symptomatic medication and/or brief interruption of infusion) also require the infusion to be permanently terminated.

CCI

Recommended actions for mild toxicity (Grade 1 events) include slowing the remaining infusion rate.

Any infusional toxicity must have resolved to < Grade 1 prior to a patient receiving the next scheduled infusion.

CCI

CCI

A large, bold, red logo consisting of the letters 'CCI' in a sans-serif font, centered on a black rectangular background.

Additional Medications

Patients may be medicated during treatment as indicated in the judgment of the treating physician to control potential infusion or hypersensitivity responses. For anaphylactic reactions, appropriate medical measures (e.g., epinephrine, antihistamines, hydrocortisone, and i.v. fluids) should be taken. Such a subject should not receive additional study drug and should be discontinued from the study.

Nausea, Vomiting and Diarrhea

Gastrointestinal toxicity may be dose limiting with this study agent. Hospital or institutional guidelines may exist and should be consulted for recommended treatment of these conditions in patients received cancer therapy. Several major oncology organizations have also provided comprehensive guidelines for optimal medical management of nausea, vomiting and diarrhea with cancer treatment. As of this writing, guidelines from these organizations are not stratified by toxicity Grade. A partial list of the major medications is provided below, but the hospital/institution guidelines or the references below should be consulted for more detailed information as to management of these conditions.

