Patients who exhibit an excessive cholinergic response to IMMU-132 treatment (e.g., abdominal cramping, diarrhea, salivation, etc.) can receive appropriate premedication (e.g. Atropine) for subsequent treatments.

Table 7: Recommended Medications for Nausea, Vomiting and Diarrhea*

Agent	Dose/Frequency	Route of administration
For Prevention of Acute Emesis:		
Palonosetron	0.075mg	
Decadron	10-20 mg 10 mg every 12 hours	PO or IV PO or IV
Granisetron	1 mg or 0.01 mg/kg 1-2 mg daily	IV PO
Ondansetron	8 mg or 0.15 mg/kg 16-24 mg daily	IV PO
Lorazepam	0.5-2 mg every 4-6 hours	PO or sublingual
Alprazolam	0.5-2 mg every 4-6 hours	PO or sublingual
For Delayed Emesis:		
Aprepitant	125 mg on Day 1 followed by 80 mg on Days 2 & 3	PO
Fosaprepitant	115 mg day 1 only	IV
For Diarrhea:		
Loperamide	4 mg initially followed by 2 mg with every episode for a maximum of 16 mg daily. Discontinue 12 hours after diarrhea resolves and normal diet is resumed.	PO
Octreotide	100-150 mcg three times daily	Subcutaneously
Fluoroquinolones (for diarrhea persisting > 24 hrs., ANC <500 or fever with diarrhea)	(e.g., ciprofloxacin 250-750 mg every 12 hours for 7 days)	PO

* Based on NCCN Antiemesis Guidelines v1.2011; Benson et al (2004) Recommended guidelines for the treatment of cancer treatment-induced diarrhea. J Clin Oncol 22:2918-26; Kris et al (2006) American Society of Clinical Oncology guidelines for antiemetics in oncology: Update 2006. J Clin Oncol 24:2932-47.

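### Aprepitant is both on the Protocol's list of CYP3A4 inhibitors to avoid (Section 4.3) and a recommended antiemetic (Table 7), and no visible text makes an exception

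*Protocol*

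**What the plan says.** Section 4.3 of the Protocol (Concomitant Medications and Procedures) ends with a paragraph on CYP3A4 inhibitors and inducers. Its rationale is that "There is a potential for altered toxicity profile from common medications and foods" that may affect how the liver metabolizes irinotecan and SN-38. The instruction is that "all patients should be recommended to avoid the following while on study therapy". Aprepitant is named in the inhibitor list with no footnote or condition. Earlier in the same section is a general allowance: "Antiemetics, anti-diarrheal medications, cytokines or blood transfusions may be administered as clinically necessary".

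Section 7.4.4 (Managing Infusional Toxicity) contains Table 7, titled "Recommended Medications for Nausea, Vomiting and Diarrhea". Under delayed emesis it lists two agents, aprepitant and fosaprepitant. The aprepitant row gives an oral regimen: "125 mg on Day 1 followed by 80 mg on Days 2 & 3". The introduction to the table says "A partial list of the major medications is provided below" and refers the reader to institutional guidelines and published references for detail.

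**The concern.** The same drug, for the same patients during the same treatment period, is recommended in one section and advised against in another. The Protocol's reason for advising against it is safety: SN-38 is the active agent that IMMU-132 delivers, and Section 7.4.4 says gastrointestinal toxicity may be dose limiting. A clinician treating delayed emesis will naturally turn to Table 7, which does not point back to Section 4.3. Two sites acting in good faith could therefore treat the same problem differently, and one of them would be going against the Protocol's own toxicity advice. What is at stake is a patient-safety instruction that should read one way. Sample size, error rates and the efficacy analysis are not involved.

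**Working it through.** The plan states no figure on this point, so the check is a comparison of text, followed by a count.

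**1. The two instructions side by side.**

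| | Section 4.3 | Table 7, Section 7.4.4 |
|---|---|---|
| Status | Recommendation to avoid | Recommendation to use |
| Who and when | All patients, while on study therapy | Patients needing delayed-emesis medication |
| Aprepitant | Named as a CYP3A4 inhibitor | Named, with dose and route |
| Qualifier or cross-reference | None | None |

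Neither is a prohibition or a mandate. They still give opposite advice on the same drug.

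**2. Does any visible text reconcile them?**
- The antiemetic allowance in Section 4.3 covers a class of drugs. The CYP3A4 paragraph that follows singles out one member of that class, so on an ordinary reading the specific caution narrows the general permission. The allowance does not mention aprepitant or the list.
- The introduction to Table 7 describes the table as partial and defers to institutional guidelines. A partial list explains why a drug might be missing. It does not explain why a drug the Protocol advises avoiding is included.
- The Table 7 footnote only cites source guidelines.
- Section 7.4.1 appears in the table of contents as "Preventative Medications", but its text is not shown, and parts of 7.4.4 are redacted. An exception could be there. Neither Section 4.3 nor Table 7 visibly points to one.

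**3. Extent within Table 7.** Agents listed: 6 for acute emesis + 2 for delayed emesis + 3 for diarrhea = 11. On the Section 4.3 list by name: aprepitant only. That is 1 of 11 overall and 1 of 2 under delayed emesis.

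**4. Context for how often antiemetics might be needed.** The adverse-event tables in Protocol Section 1, in the 10 mg/kg column (N = 109), give:
- nausea of any grade, 22%: 0.22 × 109 = 24.0, about 24 patients;
- vomiting of any grade, 17%: 0.17 × 109 = 18.5, about 19 patients;
- Grade 3 and 4 nausea and vomiting, 1% each.

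These are not counts of aprepitant users, which the documents do not give.

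**The case against.** The strongest objection is that the text most likely to hold a reconciliation is withheld. The body of Section 7.4.1 is missing, Section 7.4.4 has redacted blocks shortly before the nausea and vomiting guidance, and further redactions adjoin the supportive-care text in the synopsis and Section 3. This stands as a limit: the documents cannot show that the full Protocol lacks an exception. It does not cure the two visible passages, which read as complete in themselves and carry no pointer elsewhere.

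A second argument is that the conflict is soft. Section 4.3 speaks of common medications and foods, and its lists include grapefruit juice and St. John's wort, so it can be read as counseling on what patients routinely take. Table 7 is drawn from general guidelines, and clinical judgment governs both. It is true that neither section binds. But aprepitant is itself on the Section 4.3 list, and a clinician exercising judgment still receives two opposite recommendations from one document.

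A third argument concerns consequence. The last patient was enrolled on 22 June 2017 (SAP 3.3) and the planned final cut-off was 1 March 2019 (SAP Section 1). The documents do not say whether anyone was still on treatment at the Protocol's revision of 23 January 2020, and nothing visible reports an interaction between aprepitant and IMMU-132. This limits the reach of a correction, and the point should be weighed accordingly. The revised Protocol nevertheless still describes Phase II treatment as ongoing, and says "Patients continuing to benefit from treatment at time of study closure may be eligible to enroll in a rollover study".

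Finally, deleting aprepitant presumes that Section 4.3 is the correct side, which the documents do not establish. That is fair, and an explicit exception is an equally valid repair if the sponsor judges the use acceptable.

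**Conclusion.** The concern holds. On the visible text, the Protocol advises all patients to avoid aprepitant during study therapy and also recommends it for delayed emesis, with nothing to reconcile the two. The conflict is confined to one of 11 agents in Table 7. It merits correction because the advice is given on toxicity grounds and the repair is trivial.

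The conclusion rests on one assumption: that the withheld parts of Sections 7.4.1 and 7.4.4 contain no exception. The number of patients exposed to aprepitant and any effect on toxicity are unknown from the documents. Only patients still on treatment, in this study or after moving to a rollover study, could benefit from a correction. No efficacy result changes.

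**What to change.** Remove the aprepitant row from Table 7. If the sponsor considers its use acceptable, keep the row, state the exception explicitly in Section 4.3, and cross-refer to it from Table 7. If the row is removed, fosaprepitant is the only agent left under delayed emesis; it is not named in Section 4.3, so the Protocol should say whether the advice there extends to it. Send a short note to any site with patients still on treatment.

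The cost is one table row or one sentence with a cross-reference, plus the note to sites. No change to the statistical analysis is needed.
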